Missed or late visits: If a participant misses a scheduled visit, the visit will be rescheduled within the coming 4 weeks after the missed visit, and missed visits (i.e. no-show for a clinic appointment >3 days after the scheduled clinic appointment date) will automatically prompt an incentive “reset” to baseline (i.e. drawing one card only if the incentive condition is met). Late or early visits, defined as coming to an appointment more than 3 days of an assigned appointment date, will result in an incentive “reset” to baseline. On rare occasion, exceptions to the protocol for early, late, and missed visits may be considered at the discretion of the study coordinator and study PIs. All participants will be allowed up to 9 months from INH initiation to complete a 6-month course (180 tablets) of INH, taking missed visits/refills into account. Participants that miss ≥3 months of visit time will be considered as having failed to complete IPT.

Figure 3. Study visit flow chart: Aims 1, 2 & 3.

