5.9.1. Aim 1 analyses

The primary analysis will use multiple logistic regression models where the main independent variable is a binary variable representing assignment to economic incentives for non-heavy alcohol use (yes vs. no). The model will additionally control for assignment to incentives for IPT adherence (yes vs. no) and randomization stratification factors (i.e., gender and study cohort), to improve efficiency, and potential confounders not balanced on randomization.

The secondary outcome of treatment discontinuation due to hepatotoxicity will be analyzed using the same approach. However, if the number of hepatotoxicity events is sparse, the penalized likelihood method will be used.¹⁸¹ We will conduct similar analyses using INH adherence >90% as the outcome to evaluate whether there is an impact of economic incentives for decreasing alcohol use on IPT adherence. We will use linear regression models to examine continuous secondary outcome variables such as PEth levels, and will explore transformations for variables that are not normally distributed. If an appropriate transformation is not identified, a median regression model will be used.^{182,183}

Statistical power: With 680 participants enrolled, we anticipate 612 participants will complete both 3- and 6-month follow-up (i.e. 10% loss to follow-up). Assuming 2-sided tests, with an overall significance level of 0.05, and that 15% of controls will have no heavy drinking based on our prior data, the proposed study has 80% power to detect an absolute difference of 10% (i.e. 25% vs. 15% in the intervention and control arms, respectively) in the proportions with no heavy drinking using a chi-square test with continuity correction.

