Figure 1. Schematic of study design and aims of the Drinkers' Intervention to Prevent TB (DIPT) trial

Objectives

The DIPT trial is designed to achieve three aims. Aim 1: To determine the effectiveness of financial incentives contingent on low alcohol use (Arms 2 and 4) versus no alcohol incentives (Arms 1 and 3) to reduce heavy drinking during INH preventive therapy. The hypothesis for Aim 1 is that participants receiving incentives for negative urine EtG testing will have lower alcohol use, determined via a medium-term alcohol biomarker during INH, compared to participants receiving no alcohol incentives. Aim 2: To determine the effectiveness of financial incentives contingent on high INH adherence (Arms 3 and 4) versus no INH adherence incentives (Arms 1 and 2) to increase INH adherence during INH preventive therapy. The hypothesis for Aim 2 is that participants receiving incentives for positive POC IsoScreen testing will have better adherence to INH, determined via objective monitoring, than participants receiving no INH adherence incentives. Aim 3: To determine the effectiveness of financial incentives (Arms 2, 3, and 4) versus no financial incentives (Arm 1) on HIV virological suppression after completing their INH preventive therapy. The hypothesis for Aim 3 is that participants receiving financial incentives have higher rates of HIV virological suppression six months after INH completion.

Primary outcomes

The study has two primary outcomes. The primary outcome for Aim 1 (i.e., to estimate the effect of incentives contingent on negative urine EtG tests) is no heavy alcohol consumption over the six months of INH preventive therapy, a binary variable. This is defined as a composite outcome of both PEth <35 ng/mL and negative AUDIT-C score at both the 3- and 6-month visits. We will use standard AUDIT-C cutoffs (≥ 3 for women and ≥ 4 for men) to define heavy drinking.

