If for a given outcome no significant interaction between the two interventions is found, then no further action is required. If for a give outcome a significant interaction is found, then we will report the effect of the intervention stratified by levels of the other intervention. More specifically, if there is significant interaction between the alcohol and INH adherence intervention on the alcohol outcome, we will report two effects of the alcohol intervention, one for each level of the adherence intervention: 1) the effect of Arm 2 (alcohol intervention only) versus Arm 1 (control) and 2) the effect of Arm 4 (alcohol and INH adherence intervention) versus Arm 3 (INH adherence intervention only). Similarly, if there is if there is a significant interaction between the alcohol and INH adherence intervention on the INH adherence outcome, we will report two effects of the INH adherence intervention, one for each level of the alcohol intervention: 1) the effect of Arm 3 (INH adherence intervention only) versus Arm 1 (control) and 2) the effect of Arm 4 (alcohol and INH adherence intervention) versus Arm 2 (alcohol intervention only). Several conflicting viewpoints are expressed in the literature regarding the circumstances in which a multiple-testing correction should be used [5, 6]. For these analyses we choose not to adjust for multiplicity and use a 5% level of significance to test the effect of the intervention, while explicitly reporting a priori the comparisons that will be made.

Missing data: The primary statistical analyses will consist of a complete case analysis of individuals with non-missing outcomes. However, participants who miss the 3-month or/and 6-month visit will have missing data on the drinking outcome, which requires PEth measurements and AUDIT-C at both 3 and 6 months. To examine potential missing data mechanisms, we will compare the characteristics of the individuals who had complete data and missing data on the outcome. To examine the robustness of our findings, we will conduct a sensitivity analysis conservatively assuming that individuals who missed a study visit at 3 and/or 6 months were drinking heavily (alcohol outcome). This assumption is reasonable in this population of heavy drinkers. Finally, if it is reasonable to assume that data are missing at random and the proportion of missing data is more than 10%, we will consider using inverse probability weighting to impute the missing outcomes.

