An exploratory outcome for Aim 2 will be drug concentration (ng/mg) in a subset of small hair samples. Hair levels of INH measure long-term and cumulative exposure to INH will be used to determine if short-term increases in adherence translate to sustained changes in behavior.

Intervention-by-time-interaction. For Aims 1 and 2, we will check for the presence of intervention-by-time interaction by conducting separate analyses at months 3 and 6. We will use generalized estimating equations with an independent working correlation matrix for binary outcomes and random effect models for continuous outcomes.

Impact of COVID-related disruptions. Recruitment started on April 16 2018 and study activities were paused in March 19, 2020 due to a lockdown enforced by the Ugandan government in response to the COVID-19 pandemic. During this time, all research activities were stopped and participants on INH were contacted and instructed to stop taking their INH pills immediately, as there were no means to effectively monitor for liver toxicity. Study visits resumed on May 26, 2020 and enrollment resumed on June 16, 2020. We will conduct several descriptive statistics to examine to what extent the lockdown and the pandemic might have impacted the generalizability of the trial's findings. First, we will group the participants based on whether their scheduled INH completion date was before versus on or after March 19 2020 and will compare their baseline characteristics including measures of drinking. Second, we will perform an analysis to explore whether completion of INH before or after pandemic interruption acts as potential effect modifier of the incentive interventions.

Subgroup analyses. We will perform analyses to explore potential effect modifiers of the incentive interventions. For Aims 1 and 2, the potential moderators of interest are: sex, baseline level of alcohol use, time and risk preferences, and readiness to change . For each aim, we will fit separate models including 2-way interactions between randomization group and each potential effect moderator, as well as a model testing the interaction between the two

interventions. If an interaction is significant, subsequent stratified analyses will be conducted to explore the effect of the economic incentive interventions by categories of the moderator.

References

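### The only committed Aim 1 missing-data sensitivity analysis scores every missed month-3 or month-6 visit as heavy drinking, with no exception for visits that could not be held when due during the 2020 closure

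*SAP*

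**What the plan says.** The SAP (Primary outcomes) defines Aim 1 success as a "composite outcome of both PEth <35 ng/mL and negative AUDIT-C score at both the 3- and 6-month visits". Under Missing data, a participant who misses either visit has a missing outcome, and the primary analysis is complete case. The wording of the one sensitivity analysis the SAP commits to is, in part: "individuals who missed a study visit at 3 and/or 6 months were drinking heavily (alcohol outcome). This assumption is reasonable in this population of heavy". Inverse probability weighting is only to be considered, and only if missing at random is plausible and more than 10% of outcomes are missing.

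Under Impact of COVID-related disruptions, the SAP dates the pause from 19 March 2020, with visits resuming on 26 May and enrolment on 16 June 2020. It adds: "During this time, all research activities were stopped and participants on INH were contacted and instructed to stop taking their INH pills immediately". The planned response is to compare baseline characteristics by whether the scheduled INH completion date fell before 19 March 2020 or later, and to explore effect modification on a before/after basis. It gives no scoring rule for an outcome visit that fell due in the closure.

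Protocol section 5.5 (Missed or late visits) says that when a participant misses a visit, "the visit will be rescheduled within the coming 4 weeks after the missed visit". It also lets the coordinator and principal investigators make exceptions on rare occasions, and allows up to 9 months for the INH course.

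**The concern.** The sensitivity analysis exists to show whether the Aim 1 result is robust to missing outcomes. Scoring a missed visit as heavy drinking is a familiar conservative choice when the participant stays away. A visit that the study could not hold says nothing about that participant's behaviour, and the rule as written does not tell the two apart.

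Followed literally, it adds calendar-driven failures to both sides of the comparison. Both success proportions fall and the risk difference moves towards zero. A gap between the primary and sensitivity results might then be read as a sign of informative dropout when part of it only reflects when people enrolled. The SAP is dated August 2022, so the closure dates were known when the rule was written.

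**Working it through.** **Plan's own figure.** Protocol 5.9.1 states: "With 680 participants enrolled, we anticipate 612 participants will complete both 3- and 6-month follow-up (i.e. 10% loss to follow-up"), and claims "80% power to detect an absolute difference of 10% (i.e. 25% vs. 15% in the intervention and control arms, respectively") "using a chi-square test with continuity correction". 680 × 0.9 = 612, or 306 per factorial margin, reproduces. Recomputed continuity-corrected power at 306 per margin, two-sided 0.05, is 85.1% (270 per margin would give 80%). The stated 80% is therefore conservative. Nothing below depends on it; only the planning rates and the 10% loss are carried forward.

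**Closure and make-up.**
- 19 March to 26 May 2020 = 68 days.
- If the 4-week rule is applied, a visit due from 28 April to 25 May (28 days) could still be held once visits resumed. A visit due from 19 March to 27 April (40 days) could not.

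**Who is exposed.**
- Month-3 visits due in the closure belong to people enrolled about 19 December 2019 to 26 February 2020.
- Month-6 visits due in it belong to people enrolled about 19 September to 26 November 2019.
- The two groups do not overlap, so 2 × 68 = 136 enrolment days are exposed. Of these, 2 × 40 = 80 lie beyond the 4-week reach.

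**Share affected (assumption: even accrual of 680, none from 19 March to 16 June 2020).** Open enrolment days are 703 before the pause plus those from 16 June 2020 to the end of enrolment. That end is not stated; varying it from December 2020 to August 2022 gives 901 to 1,495 days.
- No closure visit recovered: 680 × 136/901 = 103 (15%) down to 680 × 136/1,495 = 62 (9%).
- Everything within 4 weeks recovered: 680 × 80/901 = 60 (9%) down to 680 × 80/1,495 = 36 (5%).

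**Effect on the sensitivity analysis (25% v 15%, 10% ordinary loss, closure unrelated to arm).** Let q be the share affected.
- Ordinary loss alone scored as failure: 25% × 0.9 = 22.5%, 15% × 0.9 = 13.5%, difference 9.0 points.
- Rule as written: difference = 9.0 × (1 − q).

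| Scenario | q | Difference (points) |
|---|---|---|
| No closure visit recovered | 15% to 9% | 7.6 to 8.2 |
| 4-week recovery | 9% to 5% | 8.2 to 8.5 |

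Across both scenarios the difference is 7.6 to 8.5 points, a relative shrinkage of about 5% to 15%. The intervention proportion falls from 22.5% to between 19.1% and 21.3%. The expected risk ratio stays at 25/15 = 1.67, because both proportions are multiplied by the same factor.

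**Power of the sensitivity comparison (continuity-corrected).** 76% to 82% under the rule as written, against 77% to 82% if the affected participants are left out.

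**The case against.** The strongest reply is that the rule is labelled conservative, applies only to a sensitivity analysis, and rests on a base rate. Everyone enrolled was a heavy drinker and the protocol expects only 15% to 25% to succeed, so most people with a missing outcome would have failed whatever the reason for the missed visit. The SAP's sentence can be read that way, and on that reading the reason carries over in part to closure visits. It still does not justify scoring all of them as failures, since the same planning rates imply that 15% to 25% would have succeeded.

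A second reply is that remedies already exist: the complete-case analysis leaves these people out, weighting may be considered, the protocol (5.9.5) asks for reasons for missing data to be documented where possible, and the COVID analyses look at the period. These do not close the gap. The complete-case analysis does not apply the failure rule to ordinary non-attendance while setting closure visits aside. Weighting is not a commitment. The COVID split pools those with an outcome visit due in the closure with everyone due to finish INH after it.

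Three stronger readings are tempting, and the documents do not support them.
- A reader might infer that these visits were cancelled and the outcomes cannot be scored. The SAP speaks of a pause and a resumption. Part of the closure lies within reach of the 4-week rule, that rule is written for participants who miss visits and allows exceptions, and no assessment window is set. A late assessment may well be scored.
- A reader might infer bias in favour of one arm. A calendar closure is unrelated to randomised arm.
- A reader might infer that the primary result is compromised. The failure rule is not used there.

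**Conclusion.** The point holds as a defect in a stated rule, limited to the sensitivity analysis. Followed as written, it turns missingness caused by the study into treatment failures. The expected cost is a risk difference of 7.6 to 8.5 points where 9.0 would be expected without the closure visits. The dilution is proportionate in both arms; the expected risk ratio and the primary complete-case estimate do not change.

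The size rests on assumptions that the documents cannot confirm: even accrual, an enrolment end between December 2020 and August 2022, the protocol's planning rates, and the share of closure visits later made up. The 15% end requires that none were. If most were made up and scored, the effect is small. The change should be made because it is cheap and keeps the robustness check interpretable; it is not a condition for trusting the primary analysis.

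**What to change.** In the SAP's Missing data paragraph:

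1. State that the heavy-drinking rule applies to month-3 and month-6 visits missed while the study was open.
2. State the window within which a late PEth and AUDIT-C assessment is scored as the month-3 or month-6 result.
3. Flag by due date the visits that fell between 19 March and 26 May 2020 and could not be held within that window after visits resumed. Treat them as administratively missing. Leave those participants out of the sensitivity analysis, or weight for them under missing at random, whatever their result at the other visit, so that the exclusion does not depend on drinking.
4. Keep under the heavy-drinking rule any closure visit that could have been made up after 26 May 2020 but was not attended.
5. Report administratively missing outcomes by arm.

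The cost is a few sentences and a date flag in the data set. The sensitivity analysis loses some participants: about 5% to 9% if the window is 4 weeks, and at most about 15%. Power is essentially unchanged.

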The primary outcome for Aim 2 (i.e., to estimate the effect of incentives contingent on a positive IsoScreen test) will be INH adherence measured as >90% pill-taking days by MEMS cap opening during the six-month course of INH or the time prescribed for those who were instructed to discontinue INH, a binary variable. The participants were given up to 9 months to complete a 6-month (180-pill) INH preventive therapy course. Therefore, MEMS adherence is defined as the number of pill bottle openings (no more than 1 per day counted) within a 270-day window divided by the number of prescribed doses (180, unless the participant discontinued the medication).

The outcome for Aim 3 is treated as a secondary outcome (see below).

Secondary outcomes

The secondary outcome for Aim 1 is PEth as a continuous variable measured at the 6-month visit.

The secondary outcome for Aim 2 is MEMS-measured adherence as a continuous variable (defined as the proportion of days with a bottle opening out of number of days prescribed within 9 months of randomization).

The outcome of Aim 3 is HIV virological suppression defined as an undetectable plasma HIV viral load at the 12-month visit (a binary variable). Another secondary outcome for Aim 3 will be HIV virological suppression at the 6-month visit (a binary variable).

Another secondary outcome is INH preventive therapy discontinuation due to grade 3 or grade 4 hepatotoxicity at any time while receiving INH (a binary outcome). Grade 3 hepatotoxicity was defined as AST or ALT ≥ 5 ULN or based on symptoms that met pre-specified Grade 3 criteria for hepatotoxicity. Grade 4 hepatotoxicity was defined as AST or ALT ≥ 10 ULN or based on symptoms that met pre-specified Grade 4 criteria for hepatotoxicity.

Finally, active TB during the 12 months of follow-up (a binary outcome) is also a secondary outcome. Active TB is defined as confirmed (if Xpert MTB/RIF assay positive) or suspected (based on chest x-ray findings or response to anti-TB treatment in a symptomatic and Xpert assay negative person).

Descriptive statistics

We will report the distribution of baseline covariates overall and by randomization arm. For continuous variables, we will provide the median, mean, standard deviation, 0th, 25th, 50th, 75th, and 100th percentiles. For categorical variables, we will provide frequencies and proportions. Differences between arms will not be evaluated based on statistical significance.

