and had they not received the INH adherence intervention:

$$\hat{\pi}_i(\text{Adherence Int} = 0) = \frac{\exp(\hat{\beta}_0 + \hat{\beta}_2 \text{Alcohol Int}_i + \hat{\beta}_3 z_i)}{1 + \exp(\hat{\beta}_0 + \hat{\beta}_2 \text{Alcohol Int}_i + \hat{\beta}_3 z_i)}$$

The adjusted risks of the INH adherence outcome under the INH adherence intervention and under no INH adherence intervention will be computed as:

$$\text{Risk}(\text{Adherence Int} = 1) = \frac{1}{n} \sum_{i=1}^n (\hat{\pi}_i(\text{Adherence Int} = 1))$$

$$\text{Risk}(\text{Adherence Int} = 0) = \frac{1}{n} \sum_{i=1}^n (\hat{\pi}_i(\text{Adherence Int} = 0))$$

The risk difference and risk ratio will be computed as:

$$RD = \frac{1}{n} \sum_{i=1}^n (\hat{\pi}_i(\text{Adherence Int} = 1) - \hat{\pi}_i(\text{Adherence Int} = 0))$$

$$RR = \frac{1}{n} \sum_{i=1}^n (\hat{\pi}_i(\text{Adherence Int} = 1)) / \frac{1}{n} \sum_{i=1}^n (\hat{\pi}_i(\text{Adherence Int} = 0))$$

Standard errors and confidence intervals will be derived using the delta method using the *adjrr* command in Stata [1].

Analysis of interaction between the two interventions. The DIPT trial was designed as a 2x2 factorial trial under the assumption of no interaction between the alcohol and INH adherence interventions [2]. The rationale for this assumption is that 1) if an interaction between the alcohol and INH adherence interventions exists it is expected to be synergistic, i.e., arm 4 having better outcomes than arm 3 or arm 2, and 2) only a strong synergy between the two interventions would invalidate our study design, which is not expected.

The study is not powered to detect an interaction between the two interventions as significant. However, because assessing the size of the interaction term in factorial designs is often recommended [3, 4], for each primary outcome we will test for an interaction by adding an interaction term between the two interventions in the logistic regression models defined above for the primary outcomes. More specifically, for each outcome, we will use a logistic regression model to estimate the effect of the relevant intervention including an interaction term between the two interventions and adjusting for the other intervention, and the stratification randomization factors. We will use a likelihood ratio test to test for the interaction at a 5% level of significance.

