Analyses of the secondary outcomes

For the hepatotoxicity outcome, we will use a logistic regression model including indicator variables to represent the study arms and, to improve efficiency, the randomization stratification factors (gender and study site). We will conduct 3 pairwise comparisons between each intervention (Arms 2, 3, and 4) versus the control (Arm 1).

For all other binary secondary outcomes, we will use the same statistical approach we described for the primary outcomes including a factorial analysis and a test for interaction between the interventions.

If the statistical analyses indicate an effect of the alcohol intervention versus no alcohol intervention on HIV virological suppression, we will then conduct a mediation analysis to explore the role of alcohol drinking as a potential mediator that may drive the intervention to improve HIV virologic suppression. Similarly, if the statistical analyses indicate an effect of the INH adherence intervention versus no INH adherence intervention on HIV virological suppression, we will then conduct a mediation analysis to explore the role of INH adherence as a potential mediator that may drive the intervention to improve HIV virologic suppression. More specifically, we will use methods for mediation analysis to derive the direct and indirect effects of the incentives for the primary outcomes while allowing for exposure-mediator interactions[7, 8]. We will specify a priori the list of mediator-outcome confounders.

For all continuous secondary outcomes, we will fit linear regression models. We will explore transformations for variables that are not normally distributed. If an appropriate transformation is not identified, median regression will be used. For the continuous alcohol outcomes, we will also adjust the models for the baseline drinking variables (analysis of covariance).

For all secondary outcomes, we will declare statistical significance if the p-value is < 0.05.

Missing data. For all secondary analyses we will conduct a complete case analysis.

Exploratory analyses

Exploratory outcomes. Exploratory outcomes for Aim 1 are the following continuous measures of drinking: 1) self-reported number of drinking days in the prior 30 days, 2) number of heavy drinking days (defined as ≥ 4 drinks/occasion and ≥ 5 drinks/occasion for women and men, respectively) in the prior 14 days, and 3) PEth as a continuous variable measured at other time points.

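### The SAP states Aim 3 as Arms 2, 3 and 4 against Arm 1 but analyses viral suppression by factorial margins, does not reconcile the two, and plans no interval or test for Arm 4 v Arm 1 or for all incentives pooled v Arm 1

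*SAP*

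**What the plan says.** **The question.** In its Objectives the SAP sets Aim 3 as the effectiveness of "financial incentives (Arms 2, 3, and 4) versus no financial incentives (Arm 1) on HIV virological suppression". Its hypothesis is that "participants receiving financial incentives have higher rates of HIV virological suppression six months after INH completion". Protocol 2.1 (Aim 3a) treats the arms as three separate interventions, each against Arm 1. Protocol 5.9.3 makes these three pairwise contrasts the ones of main interest, with Hochberg adjustment and a power statement at alpha 0.0167.

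**The analysis.** Under Analyses of the secondary outcomes, the SAP plans three comparisons with Arm 1 for hepatotoxicity only. Every other binary secondary outcome, including suppression at months 12 and 6, gets "the same statistical approach we described for the primary outcomes including a factorial analysis and a test for interaction between the interventions". The mediation paragraph in that section names the suppression effects as alcohol intervention v none and INH adherence intervention v none, so the margins are plainly meant. Significance for all secondary outcomes is p < 0.05.

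**The interaction rule.** For the primary outcomes the SAP says: "If for a given outcome no significant interaction between the two interventions is found, then no further action is required". After a significant interaction it reports Arm 2 v 1 and Arm 4 v 3 (alcohol outcome), or Arm 3 v 1 and Arm 4 v 2 (adherence outcome), without multiplicity adjustment. It also says: "The study is not powered to detect an interaction between the two interventions as significant".

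**What is disclosed.** The SAP says that the Aim 3 outcome is now secondary. It does not say that the contrast differs from the one in its own Objectives.

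**The concern.** The objective can be read as three contrasts with Arm 1 or as one pooled contrast of any incentive against none. The planned margins are neither. In the alcohol margin the comparator is Arms 1+3, and in the adherence margin it is Arms 1+2, so half of each comparator group is offered an incentive.

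At stake is what the report will contain. A reader who takes Aim 3 at its word expects an estimate for both incentives together against none, and for each incentive alone against none. The SAP plans no interval or test for the first on any route. The second would appear only after a significant interaction, if the rule written for the primary outcomes applies here too. The only power figure in the documents for this outcome describes contrasts that the SAP does not plan to report as a matter of course.

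**Working it through.** **Inputs.** 680 enrolled, allocated 1:1:1:1 (protocol 5.9.1 and 5.3). From protocol 5.9.3: 15% loss by month 12, 67% suppression in Arm 1, 84% as the example in the incentive arms, alpha 0.0167, continuity-corrected chi-square. Two-sided testing is stated for Aim 1 and assumed here. Evaluable: 680 × 0.85 = 578, or 144.5 per arm and 289 per margin.

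**1. Reproduce the protocol's figure.** For n per group and mean proportion p̄,

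power = Φ{ [ |p2 − p1| − 1/n − z·√(2p̄(1 − p̄)/n) ] / √([p1(1 − p1) + p2(1 − p2)]/n) }.

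With 0.67 v 0.84, n = 144.5 and z = 2.394: (0.17 − 0.0069 − 2.394 × 0.0506)/0.0496 = 0.85, so power is 80.1%. The stated 80% is right for a pairwise contrast.

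**2. The same example seen through the margins.** If all three incentive arms reached 84%, each comparator would be (67 + 84)/2 = 75.5%, a difference of 8.5 points. With n = 289 and z = 1.96: (0.085 − 0.0035 − 1.96 × 0.0334)/0.0332 = 0.48, so power is 68.5% (72.1% without the correction). The protocol gives 84% only as an example. The margin difference detectable with 80% power, corrected and with no interaction, is 10.7 points from a 67% comparator and 10.1 points from 72%.

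**3. Is overall power lost?** Simulation: 60,000 trials per scenario, arms of 144/145/145/144, main-effects logistic model with standardised risk differences, likelihood-ratio interaction test at 5%, no stratification covariates. The SAP route here assumes that the interaction rule carries over. Chance of finding some incentive effect:

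| Arms 1/2/3/4 (%) | SAP route | Three pairwise, Hochberg |
|---|---|---|
| 67/84/84/84 | 96.7% | 97.2% |
| 67/77/77/87 | 97.2% | 96.4% |

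The routes are about equal.

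**4. What is missing.** RD(alcohol) + RD(adherence) = [(p2 + p4) − (p1 + p3)]/2 + [(p3 + p4) − (p1 + p2)]/2 = p4 − p1. With equal arms, the Arm 4 v 1 point estimate is therefore the sum of the two reported margins (approximately so once covariates enter). The missing items are its interval and test. The 95% half-width at 67% v 87% is 1.96 × √[(0.2211 + 0.1131)/144.5] = 9.4 points; at 67% v 84% it is 9.7. Pooled Arms 2+3+4 v 1 would have 98.3% power at 67/84/84/84 and 87.5% at 67/77/77/87.

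**5. If the interaction rule carries over, when do Arm 2 v 1 and Arm 3 v 1 appear?**

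| Arms 1/2/3/4 (%) | Interaction on the logit scale | Test significant | Mean Arm 2 v 1 when it is (true value 10) |
|---|---|---|---|
| 67/77/77/84.7 | none | about 5% | about 10 |
| 67/77/77/87 | synergistic | 7.8% | 5.1 |
| 67/77/77/77 | antagonistic | 25.8% | 14.4 |

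The first row is the SAP's own assumption: odds of 0.77/0.23 = 3.348 and 0.67/0.33 = 2.030 give an Arm 4 odds of 3.348²/2.030 = 5.52, or 84.7%. At 67/84/84/84, also antagonistic, the test is significant in 60.3% of trials.

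**The case against.** The strongest reply is that nothing is hidden and nothing is invalid. The SAP separates hepatotoxicity from all other binary secondary outcomes, and its mediation text names the margin effects for suppression. It sets p < 0.05 for secondary outcomes. Where it describes the contrasts that follow a significant interaction, it says that it does not adjust for multiplicity, and why. The margins are efficient under the no-interaction assumption on which the trial was designed. All of this stands. What it leaves open is that the objective in the same SAP asks a different question, and no sentence connects the two.

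Three stronger readings are tempting, and the documents do not support them:

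- *The plan loses power.* It does not: the two routes find some incentive effect about equally often.
- *The SAP certainly withholds the single-incentive contrasts unless the interaction is significant.* The detailed rule is written for the two primary outcomes. It reaches suppression only if the phrase about using the same approach carries the reporting rule with it, which is likely but not stated.
- *Reporting only after a significant interaction biases those contrasts.* Under the SAP's own assumption the average is not shifted. The means of 14.4 and 5.1 points arise under antagonism, or under synergy on the logit scale. The SAP expects any interaction to be synergistic, which counts against the antagonistic cases.

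It is also fair that a new power figure for a secondary outcome changes little, and that protocol 5.9.3 does plan Arm 4 v 1. The omission is the SAP's alone.

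**Conclusion.** The point holds as a mismatch within the SAP between the stated Aim 3 question and the planned contrasts, together with the absence of any interval or test for Arm 4 v 1 or for pooled incentives v none. That part rests on the text and needs no assumption about effect sizes.

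If the interaction rule does carry over, Arm 2 v 1 and Arm 3 v 1 would each be reported in only about 5% of trials under no interaction. That is a gap in reporting, not a bias. The numerical results assume 578 evaluable participants in near-equal arms, 67% suppression in Arm 1 and no stratification covariates.

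A reader might infer an undisclosed switch that weakens the trial. The documents do not bear this out: the margins are stated for this outcome, its secondary status is declared, and overall power is kept. Priority is minor to moderate.

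**What to change.** **Preferred.** Keep the factorial margins as the main analysis. For suppression at months 12 and 6, also report Arms 2, 3 and 4 each against Arm 1 with 95% intervals, whatever the interaction test shows. Use the arm-indicator logistic model that the SAP already specifies for hepatotoxicity. State whether the protocol's Hochberg adjustment applies to these contrasts, and whether the objective means three contrasts or one pooled contrast.

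*Cost:* a few sentences and three more contrasts per time point; no new data. The single-incentive contrasts have less power than the margins (about 43% with Hochberg against 83% at 67/77/77/87), so they should supplement the margins and not replace them.

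**Alternative.** Restate the SAP's Aim 3 objective and hypothesis as the two margin contrasts. Note that the pairwise power figure in protocol 5.9.3 no longer applies, and that about 10 to 11 points per margin are detectable with 80% power. Give Arm 4 v 1 with its interval as a descriptive estimate.

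*Cost:* wording and one interval per time point.
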